#### 6. STATISTICAL CONSIDERATIONS

##### 6.1. Descriptive Statistics

###### (1) Non-PK related

Continuous data will be summarized descriptively using the number in the analysis set (N), the number of observations (n), mean, standard deviation (SD), median, minimum and maximum. Categorical data will be summarized using frequency counts and percentages. The denominator for the percentages will be the total number of subjects in the treatment group and analysis population being presented, unless otherwise specified.

For numerical variables, change from baseline will be calculated as the post-baseline value minus the baseline value. If percentage change from baseline is required, then percentage change from baseline will be calculated as the change from baseline divided by the baseline value, multiplied by 100. If baseline value cannot be determined for a particular variable, the change from baseline and percentage change from baseline will not be calculated.

Unscheduled visits will not be displayed in by-visit summary tables, but will be included in the data listings.

All data will be listed. Listings will include treatment, scheduled, unscheduled, retest and early

discontinuation data. No visit windowing will be performed for this study.

## **(2) PK related**

Plasma concentrations will be summarized descriptively using N, n, mean, SD, median, minimum and maximum.

The plasma and urine PK parameters will be summarized descriptively using N, n, arithmetic mean, SD, median, minimum, maximum, CV%, geometric mean and geometric CV%  
CV% and Geometric CV% will be calculated as follows:

$$CV\% = \frac{\text{standard deviation}}{\text{arithmetic mean}} \times 100$$

$$\text{Geometric CV\%} = \sqrt{[\exp(\sigma^2) - 1]} \times 100$$

where  $\sigma$  represents the standard deviation computed on the natural logarithmic transformed concentrations.

## **6.2. Statistical Tests**

Not Applicable for this study.

# **7. DATA CONVENTIONS**

## **7.1. Analysis Variable Definitions**

### **7.1.1. Study Subjects**

#### **7.1.1.1. Protocol Deviations**

Protocol deviations will be identified and documented during a data review prior to database lock and confirmed by database lock. Major protocol deviations will be defined as deviations that may significantly impact the completeness, integrity, accuracy, and/or reliability of the study data and may significantly affect a subject's rights, safety, or well-being.

#### **7.1.1.2. Demographic and Other Baseline Characteristics**

##### **(1) BMI**

BMI will be recalculated using the formula below and reported to 1dp.

$$\text{BMI (kg/m}^2\text{)} = \text{weight at screening (kg)} / \{\text{height at screening (m)}\}^2$$

##### **7.1.1.3. Medical History**

Medical history will be coded according to the Medical Dictionary for Regulatory Activities (MedDRA) version 20.0 or later.

#### **7.1.1.4. Prior or Concomitant Medication**

Medications will be coded according to the World Health Organisation Drug Dictionary (WHO-DD) SEP 2017 version.

##### **(1) Prior Medication**

Medication taken within 2 weeks of Screening will be recorded in the subject's source documents as prior medication.

##### **(2) Concomitant Medication**

Concomitant medication is defined as any medication, other than the IMP, which is taken during the study, including prescription, herbal and over the counter medications.

### **7.1.2. Safety Assessments**

#### **7.1.2.1. Adverse Events**

Adverse events will be coded according to the MedDRA version 20.0 or later.

##### **(1) Treatment Emergent Adverse Events/ Treatment Emergent Serious Adverse Events (TEAEs/TESAEs)**

AEs/SAEs will be classified as 'treatment-emergent' if they arise following the first administration of IMP or if a pre-dose AE increases in severity following dosing.

##### **(2) Adverse Drug Reaction**

A TEAE is considered an "adverse drug reaction" if it has been assessed as having a "reasonable possibility" in relationship to the study drug.

##### **(3) Duration of Adverse Events**

Duration of Adverse Events (days) = AE stop date – AE start date + 1

#### **7.1.2.2. Laboratory Tests**

##### **(1) Laboratory values below the limit of quantification**

1/2 LLOQ will be used for BLQ (below the limit of quantification) data in summary statistics.

#### **7.1.2.3. 12-Lead ECG**

##### **(1) Criteria for pre-defined limit**

12-lead ECG:

- QTcF : > 450 msec, QTcF > 480 msec, QTcF > 500 msec
- Increase from baseline in QTcF : > 30 msec, > 60 msec

### **7.1.3. Pharmacokinetics Evaluation**

#### **7.1.3.1. Plasma Concentration**

For the calculation of the summary statistics, concentration values reported as below the limit of quantification (BLQ) will be set to 0. Only valid PK data will be included in the summary tables or figures.

### 7.1.3.2. Pharmacokinetic Parameters

For the calculation of PK parameters, actual sampling time (in hours rounded to 2 decimal places) relative to dosing should be used. Concentration below the limit of quantification (BLQ) will be imputed with a value of 0. For calculation of AUCs, missing data will be treated as if the respective sample never had been scheduled for the calculation by the linear-linear trapezoidal rule.

For Ae, Ae% and CLR, geometric mean and geometric CV% will be calculated only when all the individual Ae, Ae% and CLR is greater than 0 at each sampling time point.

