- Serology testing for hepatitis B surface antigen, hepatitis B core antibody, hepatitis C antibodies and HIV 1/2 antibodies.
- Female subjects only (Part 4). A serum pregnancy test will be performed at Screening and a urine pregnancy test at all other time points.
- Females only (Part 4). The sample taken for biochemistry analysis will be used to measure FSH.
- A full physical examination will be performed at Screening and Day 15 FU. At other times, a targeted (symptom driven) physical examination of relevant body system(s) will be performed following physician assessment if the subject reports feeling unwell or an adverse event.
- Continuous 12-lead Holter data will be obtained from subjects in Part 1. Continuous ECG will be collected from approximately 24 hours prior to dosing (Day -1) to 24 hours post-dosing (Day 2). Electrocardiogram extractions will occur at each PK blood sampling time point during this period.
- A 12-lead ECG (heart rate and cardiac intervals: PR, QRS, QT and QTcF) will be performed at Day -1 (-0.5, 1, 2, 3, 8) and Day 1 (pre-dose, 1, 2, 3, 8 hours post-dose) and Day 2 (24 hours post-dose).
- PK blood samples for MT-6345 will be taken at pre-dose, 0.5, 1, 1.5, 2, 3, 4, 5, 6, 8, 12, 16, 24, and 48 hours post-dose. Subjects will return for outpatient visits and PK blood samples will be taken at 72 (Day 4), 120 (Day 6), 192 (Day 9) and 336 hours (Day 15 FU) post-dose.

Europe/Mitsubishi Tanabe Pharma Europe Ltd  
STUDY PROTOCOL

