**6.4 Pharmacokinetic assessments**

In single-dose parts, blood samples for MT-6345 will be collected at pre-dose, 0.5, 1, 1.5, 2, 3, 4, 5, 6, 8, 12, 16, 24 and 48 hours post-dose. Subjects will return for outpatient visits and PK blood samples will be taken at 72 (Day 4), 120 (Day 6) and 192 hours (Day 9) post-dose and at the Day 15 Follow-up Visit (336 hours).

In Part 3, blood samples for MT-6345 will be collected on Day 1 (pre-dose and at 0.5, 1, 1.5, 2, 3, 4, 5, 6, 8, 12 and 16 hours post-dose), Day 2 to the day before the last day of dosing (pre-dose), the last day of dosing (pre-dose and at 0.5, 1, 1.5, 2, 3, 4, 5, 6, 8, 12 and 16 hours post-dose), and on the last day of dosing +1 (24 hours post last dose), last day of dosing +2 (48 hours post last

STUDY PROTOCOL

dose) and last day of dosing +3 (72 hours post last dose). Subjects will return for outpatient visits and PK blood samples will be taken 5 and 8 days after the last dose (120 and 192 hours after last dose) and Follow-up 14 ± 1 days after last dose (336 hours after last dose).

The timings of all PK and [REDACTED] may be subject to change based on the ongoing review of data. Additional blood samples may be taken from each subject; however, the maximum volume of blood withdrawn per subject will not exceed the limit detailed in Section 6.7. Any changes to the scheduled times of PK or [REDACTED] will be agreed between the Sponsor and Investigator and documented in the TMF.

Not all cohorts will have samples taken for [REDACTED]. Samples for [REDACTED] will be taken from at least two cohorts in Part 3 and these cohorts will be selected based on emerging PK data from Part 1.

Sample handling details will be described fully in a separate document.

Contingency samples will be retained at [REDACTED] Phase I unit and shipped at the request of the Sponsor. If not required, the contingency samples will be destroyed only upon the written request of the Sponsor.

Blood and urine samples will be packed in dry ice and sent by courier from [REDACTED] [REDACTED]. (PK samples) and [REDACTED], MTPC [REDACTED]).

The analysis will be performed only on samples from subjects receiving active drug. Results from the [REDACTED] will be reported separately.

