## 11 SOFTWARE

All statistical analyses will be performed using SAS® version 9.4 or higher.

The PK parameters will be calculated using WinNonlin® software (version 6.3 or later).

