## Appendix 1 Pharmacokinetic Parameter Calculations

Actual blood sampling times will be used in the calculation of pharmacokinetic parameters

All concentrations below the LLOQ will be set at zero for pharmacokinetic calculations

When Kel is missing (or cannot be determined),  $t_{1/2}$ ,  $AUC_{0-\infty}$ ,  $AUC\%_{ex}$ , CL/F, MRT, Vz/F and Vss/F will not be calculated.

PK Parameter Calculations		
Parameters	Unit	Calculation
$C_{max}$	ng/mL	will be determined by visual inspection
$AUC_{0-\infty}$	ng·h/m L	$AUC_{0-\infty} = AUC_{0-last} + AUC\%_{ex}$
$AUC\%_{ex}$	ng·h/m L	$AUC_{exp} = C_{last} / Kel$ $C_{last}$ : last measurable concentration
$AUC_{0-last}$	ng·h/m L	will be calculated using the linear trapezoidal method and actual times $AUC_{0-la} = \sum_{i=1}^n \frac{t_i - t_{i+1}}{2} (C_{i-1} + C_i)$
$t_{max}$	h	Measured time of $C_{max}$
$t_{1/2}$	h	$t_{1/2}$ will be determined as: $t_{1/2} = \log_e (2) / Kel$
Kel	/h	
The exponential rate constant of the terminal phase, Kel, will be estimated by log-linear regression, if determinable. The number of data points included in the regression will be determined by visual inspection. Wherever possible, a minimum of 3 data points will be used in the estimation of Kel.
 
During the analysis, this calculation method repeats regressions using the last three points with non-zero concentrations, then the last four points, last five, etc. The time of maximum concentration (tmax) will be excluded from the estimation of Kel.
 
Points with a value of zero for the dependent variable are excluded.
 
For each regression, an adjusted <math>R^2</math> is computed
 $Adjusted R^2 = 1 - \frac{(1 - R^2) \times (n - 1)}{(n - 2)}$

		
where n is the number of data points in the regression and <math>R^2</math> is the square of the correlation coefficient.
 
The regression with the largest adjusted <math>R^2</math> is selected to estimate <math>K_{el}</math>, with these caveats:
 
 
- If the adjusted <math>R^2</math> does not improve, but is within 0.0001 of the largest adjusted <math>R^2</math> value, the regression with the larger number of points is used.
 
- <math>K_{el}</math> must be positive, and calculated from at least three data points.
 

CL/F	L/h	$CL/F = Dose / AUC_{0-\infty}$
MRT	/h	$MRT = AUMC_{0-\infty} / AUC_{0-\infty}$ AUMC 0-∞ : area under the first moment curve extrapolated to infinity

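### The linear trapezoidal rule, applied through late sampling gaps of 24 to 144 h, overstates AUC0-last and AUC0-inf and understates CL/F by roughly 1-6% under assumed half-lives and LLOQs

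*SAP*

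**What the plan says.** SAP 7.1.3.2 removes a missing sample from the time grid, as though it had not been planned, "for the calculation by the linear-linear trapezoidal rule". Appendix 1 says that AUC0-last "will be calculated using the linear trapezoidal method and actual times". Neither place gives a logarithmic rule for the declining phase, and no rule is stated for AUMC.

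The footnotes to Protocol Table 2 put the single-dose samples at "pre-dose, 0.5, 1, 1.5, 2, 3, 4, 5, 6, 8, 12, 16, 24, and 48 hours post-dose", and then "PK blood samples will be taken at 72 (Day 4), 120 (Day 6), 192 (Day 9) and 336 hours (Day 15 FU) post-dose". Protocol 6.4 gives Part 3 the same late times after the last dose.

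Appendix 1 estimates Kel by log-linear regression on at least three points, choosing the best adjusted R-squared. It adds that "The time of maximum concentration (tmax) will be excluded from the estimation of Kel" and that "All concentrations below the LLOQ will be set at zero for pharmacokinetic calculations". AUC0-inf is AUC0-last plus Clast/Kel, and CL/F is dose divided by AUC0-inf.

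**The concern.** The plan uses two shapes for the same part of the curve. To extrapolate beyond the last sample it assumes exponential decline. Between the late samples, up to 144 h apart, it joins the points with straight lines. Over an exponential decline every such line lies above the curve, so each late segment is overestimated and the errors add up. AUC0-last and AUC0-inf are then too high, and CL/F, which divides by AUC0-inf, is too low.

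The missing-sample rule makes this worse. One missed outpatient visit merges two gaps into one, and the overestimate grows faster than the gap. A missed visit then becomes a sizeable error in that subject's AUC and clearance. In a first-in-man study these parameters are secondary endpoints, and they are summarised and listed.

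**Working it through.** **Inputs from the documents.** Linear rule; sampling times; Kel and BLQ handling; AUC0-inf and CL/F definitions, all as above. The plan states no figure for this error, so there is none to reproduce.

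**Assumed inputs.** The readable text gives no half-life, absorption rate or LLOQ. The check uses noise-free one-compartment oral profiles with half-life 4-96 h, ka 0.5-2 /h and LLOQ/Cmax 0.0001-0.05.

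**Step 1: one interval.** For exponential decline at rate k over a gap d, with x = kd:

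linear area / true area = (x/2)(1 + e^-x)/(1 - e^-x)

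At a half-life of 48 h, k = 0.6931/48 = 0.01444 /h. The excess is 1.0% for a 24 h gap, 4.0% for 48 h, 8.9% for 72 h and 33.7% for 144 h.

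**Step 2: hand example.** Take C(t) = 100 x 2^(-t/48). The true AUC0-inf is 100/0.01444 = 6924.9.

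| Interval (h) | Linear | Exact | Excess |
|---|---|---|---|
| 24-48 | 1448.5 | 1434.2 | 14.3 |
| 48-72 | 1024.3 | 1014.1 | 10.1 |
| 72-120 | 1272.8 | 1224.2 | 48.6 |
| 120-192 | 861.4 | 791.4 | 70.0 |
| 192-336 | 506.3 | 378.7 | 127.5 |

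The total excess is 270.6, and 270.6/6924.9 = +3.9%. CL/F changes by 1/1.039 - 1 = -3.8%.

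**Step 3: remove the 120 h sample.** The interval 72-192 h becomes one segment: linear 2496.3, exact 2015.5, excess 480.8. The total is 14.3 + 10.1 + 480.8 + 127.5 = 632.7, or +9.1%.

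**Step 4: full profiles.** With absorption included, ka 1/h, Cmax/LLOQ 500 and Kel as in Appendix 1, the error in AUC0-inf against the exact area is:

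| Half-life (h) | Last quantifiable (h) | Linear | Linear-up/log-down | Linear, 120 h missing |
|---|---|---|---|---|
| 8 | 72 | +5.1% | -0.3% | not applicable |
| 24 | 192 | +4.0% | -0.1% | +12.1% |
| 36 | 192 | +2.9% | -0.1% | +10.1% |
| 48 | 336 | +3.9% | 0.0% | +9.2% |
| 72 | 336 | +2.9% | 0.0% | +5.7% |

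With the 120 h sample missing, linear-up/log-down stays within 0.1% for half-lives of 24-72 h.

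**Step 5: range over the assumptions.** Over 264 combinations the linear rule always gave the higher AUC0-inf: +0.8% to +6.0% against linear-up/log-down, median +3.4%. CL/F was 0.8% to 5.7% lower. In the 230 combinations with a quantifiable sample beyond 24 h, the AUC0-inf range is +1.1% to +6.0%, of which the late gaps alone supply 1.1% to 5.1%. For half-lives of 24-72 h it is +1.1% to +4.4%. Eight two-compartment profiles gave +1.1% to +4.1%.

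**Step 6: what is not affected.** AUC0-24h and AUC0-tau end at 24 h. The choice of rule changes AUC0-24h by at most 0.16% at half-lives of 24-72 h. The dose-proportionality slope moves by less than 0.004.

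**Step 7: fed versus fasted.** Under Protocol 5.2.4.1 the Part 2 cohort skips the follow-up visit after its first period, so fasted profiles stop at 192 h and fed profiles can reach 336 h. In the hand example, dropping the last segment gives (6924.9 + 270.6)/(6924.9 + 143.0) = 1.018 with no true food effect. At Cmax/LLOQ 500, the 336 h sample is quantifiable only above a half-life of about 336/log2(500) = 37 h. Below that the ratio is 1.000, and above it at most about 1.02.

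**The case against.** The linear rule is a recognised choice, pre-specified and the same in the SAP body and appendix. There is no contradiction or omission here. The error is small and rests on assumed, noise-free profiles. If nothing is quantifiable after 24 h, the late gaps contribute nothing. The error also largely cancels in ratios whose profiles end at a similar time. All of this stands, and it keeps the point minor. It does not change the direction of the error, and it does not answer the missing-sample case.

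A reader might infer more than the documents support:

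- **A fixed bias of 3-5%.** Only about 45% of the combinations in the grid fall in that band. Without a half-life and LLOQ, only a conditional range can be given.
- **A threat to dose escalation.** The exposure limit is defined on AUC0-24h, which does not use the late gaps.
- **A false food effect.** The shift needs a quantifiable 336 h sample. SAP section 10 lists the linear mixed model as not done, so only descriptive summaries are touched, and six subjects returned for Part 2, active and placebo together.
- **Distorted dose proportionality.** The slope change is negligible.
- **Wrong clearance values used in later work.** The study was terminated, and nothing in the documents describes later use of these estimates.

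**Conclusion.** The point holds as a cheap improvement, not as an error in the plan. With quantifiable samples beyond 24 h, the linear rule overstates AUC0-last and AUC0-inf and understates CL/F by roughly 1-6%. If the 120 h sample is missing, AUC0-inf is about 6-12% too high at an assumed half-life of 24-72 h and Cmax/LLOQ 500. The direction follows from the plan's own log-linear terminal phase. The size depends on half-life, LLOQ and absorption rate, which are assumptions here. In a descriptive comparison, the fed/fasted ratio shifts by at most about 2%.

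**What to change.** In SAP 7.1.3.2 and Appendix 1, specify linear-up/log-down for AUC0-last, AUC0-inf and AUMC: linear up to Cmax, logarithmic between declining non-zero concentrations. At a minimum, keep the linear rule and report linear-up/log-down as a sensitivity analysis for AUC0-last, AUC0-inf and CL/F.

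The change needs no new data, only SAP wording and a recalculation. The SAP names WinNonlin but does not describe its AUC options, so the analyst should confirm the setting in the version used. The one drawback is that final AUCs may differ slightly from interim dose-review AUCs, if those used the linear rule. A footnote can explain this.

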### 7.1.4. Other Evaluations

For the steady state evaluation, in the case where the trough concentrations for either numerator or denominator is BLQ, the ratio will not be calculated for that day (in this case the result will be shown as not calculated [NC] in the listings and will be excluded from the summary statistics).

## 7.2 Analysis Visit Definitions

### (1) Non-PK related

No visit windowing will be performed for this study.

Unless otherwise specified, baseline will be the last observed value of the parameter of interest prior to the first intake of study drug (this includes unscheduled visits). For other visits, if there are multiple data in a window, the closest data to nominal day will be used. If the distance to the nominal day is the same, the data of later date will be used.

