**10.3.4.2 Vital signs and electrocardiograms**

Vital signs and 12-lead ECG variables and changes from baseline will be summarised (N, n, mean, SD, median, minimum and maximum) at each time point for each study Part by dose level and by fed state, gender and race category, where appropriate.

The baseline for the vital sign parameters and 12-lead ECG measurements will be the last valid assessment obtained on Day 1 prior to the administration of double-blind IMP.

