## 1. INTRODUCTION

This statistical analysis plan (SAP) is based on the final protocol (v2.0) dated 12-DEC-2018. The plan covers statistical analysis, tabulations and listings of the study data to investigate the safety, tolerability and pharmacokinetics of single and multiple ascending doses of MT-6345 compared to placebo in healthy subjects.

Any statistical analysis details described in this document supersede any description of statistical analysis in the protocol.

This study was terminated due to brain changes in male rats in the 13-week tox study. Subjects were enrolled in only Part 1, Part 2 and Part 3. Some assessments which were not performed are grayed out in this SAP.

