## Part 2: Food effect

A single cohort from Part 1 (anticipated to be Cohort 3; [REDACTED] MT-6345) will be selected to return for a second treatment period to investigate the effect of food (after a Food & Drug Administration [FDA]-approved high-fat breakfast)[14] on the PK of MT-6345. There will be a minimum of 15 days between the last dose administration in Part 1 and the first dose administration in Part 2. Subjects in Part 2 will receive the same dose (active or placebo) that they received in Part 1.

The dose and cohort selected for Part 2 will not be confirmed until safety, tolerability and PK data from the intended dose level in Part 1 has been reviewed and deemed acceptable. The intention is for all 8 subjects to be dosed sequentially on the same day.

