### 8.2.4 12-Lead ECGs

Absolute values will be summarized and presented at each timepoint for each study part by dose level and by fed state will for the following parameters.

- PR (msec)

- QRS (msec)
- QT (msec)
- QTcF (msec)
- Overall evaluation

The frequency counts and percentages of subjects with 12-lead ECG values outside pre-defined limits will be summarized

All data will be listed.

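### SAP 7.2 gives Part 2 no baseline of its own, so read literally the fed-period QTcF increases (>30, >60 ms) are measured from a Part 1 pre-dose value

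*SAP*

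**What the plan says.** - **Baseline in the SAP (7.2, non-PK data).** Where no other rule is given, "baseline will be the last observed value of the parameter of interest prior to the first intake of study drug (this includes unscheduled visits".
- **Baseline in the protocol (10.3.4.2).** For vital signs and 12-lead ECG it is "the last valid assessment obtained on Day 1 prior to the administration of double-blind IMP".
- **Precedence (SAP 1).** "Any statistical analysis details described in this document supersede any description of statistical analysis in the protocol".
- **Part 2 (SAP 3.1.1 and 3.3.2).** One Part 1 cohort returns and takes the same treatment, active or placebo, after a high-fat breakfast. "There will be a minimum of 15 days between the last dose administration in Part 1 and the first dose administration in Part 2". Six subjects returned; they are not counted again as exposed.
- **Output that uses baseline (SAP 7.1.2.3 and 8.2.4).** The pre-defined limits include "Increase from baseline in QTcF : > 30 msec, > 60 msec", and "The frequency counts and percentages of subjects with 12-lead ECG values outside pre-defined limits will be summarized".
- **Declared changes (SAP 10).** The change-from-baseline summaries for vital signs, ECG and laboratory tests were dropped. A changed baseline definition is not listed.

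**The concern.** For someone who returns for Part 2, the first intake of study drug is the Part 1 dose. The SAP rule therefore points to a Part 1 reading as the reference for ECGs recorded after the Part 2 dose. The protocol's Day 1 pre-dose rule fits a separate baseline for each period, because the schedule covering Part 2 has its own Day 1 pre-dose ECG. The SAP overrides that rule without saying that it has changed it.

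With the change-from-baseline summaries gone, the two QTcF-increase categories are the only ECG output in the readable SAP that still depends on baseline. ECG parameters belong to the primary safety endpoints. At stake is whether a fed-period flag reflects the fed dose or a difference between two pre-dose readings taken at least 15 days apart.

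**Working it through.** The plan gives no figure to reproduce. The check applies the rule to the Part 1-Part 2 sequence, then illustrates the size.

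**1. Lag.** The Part 1 baseline precedes the Part 1 dose, and the doses are at least 15 days apart. Minimum lag to each Part 2 ECG is 15 + h/24 days:
- 1 h: 15.04; 2 h: 15.08; 3 h: 15.12; 8 h: 15.33; 24 h: 16.0 days
- Follow-up on Day 15: 15 + 14 = 29 days, or 28 at the early edge of the ±1 day window

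Every Part 2 post-dose reading is thus at least 15 days and one dose (active or placebo) after its reference.

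**2. Identity, no assumption needed.** For one subject:

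SAP increase = (Part 2 post-dose − Part 2 pre-dose) + (Part 2 pre-dose − Part 1 pre-dose)

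The first bracket is the within-period increase; the second is the shift. A within-period rise of 20 ms is counted as >30 ms when the shift exceeds +10 ms. A rise of 40 ms is missed when the shift is −10 ms or lower. If each pre-dose value has an assumed between-day SD s, the shift has SD √2·s, and either error has probability 1 − Φ(10/(√2·s)):
- s = 5 ms: 0.08
- s = 10 ms: 0.24
- s = 15 ms: 0.32

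**3. Chance of a >30 ms flag with no drug effect.** The SDs are assumptions. Model: reading = day effect + within-day error, with independent day effects on different days. A subject is flagged when the largest post-dose reading minus one baseline reading exceeds 30 ms. Times follow the schedule: 1, 2, 3 and 8 h on Day 1, 24 h on Day 2, and Follow-up on Day 15. Simulated with 2,000,000 subjects per row:

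| Between-/within-day SD (ms) | Readings | Part 2 baseline | Part 1 baseline | Ratio |
|---|---|---|---|---|
| 5 / 7 | 1-24 h | 1.1% | 2.5% | 2.3 |
| 8 / 7 | 1-24 h | 2.7% | 7.0% | 2.6 |
| 10 / 8 | 1-24 h | 6.0% | 13.1% | 2.2 |
| 5 / 7 | plus Follow-up | 1.7% | 3.0% | 1.8 |
| 8 / 7 | plus Follow-up | 4.5% | 8.3% | 1.8 |
| 10 / 8 | plus Follow-up | 9.5% | 15.5% | 1.6 |

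For >60 ms the chance per subject is at most about 0.2% in every row, with either baseline.

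**4. Search for an exception.** SAP 8.2.1 has a Part 2 rule for adverse events, which moves attribution to Part 2 at the Part 2 dose. No matching rule for baseline appears in the readable SAP.

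**The case against.** **Intent.** The rule opens with a proviso, and first intake could have been meant per part. Outputs are organised by study part, SAP 9.3 lists a Day 1 pre-dose visit for Parts 1 and 2, and adverse-event attribution restarts at the Part 2 dose. This stands as evidence that the programmers may have used the Part 2 value. None of it states a baseline, so two programmers could derive different counts. The documents do not show that the Part 1 value was in fact used.

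**Size.** A reader might infer a much larger inflation. If all five readings from 1 to 24 h are treated as sharing the baseline's day, the same SDs give 0.6-1.7% against 2.4-11%, a ratio of about 4 to 11. The schedule does not support that, because the 24 h reading falls on Day 2. Even a period-specific baseline is then compared with another day, and the ratio drops to the range in the table.

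**Fed against fasted.** A reader might infer that the fed and fasted counts would be strictly comparable but for this rule. They would not. Fasted 24 h readings are also taken on a different day from their baseline. Under Protocol 5.2.4.1 the returning cohort skips the Part 1 Follow-up, so the fed period has an extra late ECG whichever baseline is used. Nor does SAP 8.2.4 say that the limit counts are split by fed state; it says so for absolute values. The split is implied by the Part 2 table layout in SAP 9.2.

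**Consequence.** There are no statistical tests. The absolute limits (>450, >480, >500 ms) and the by-timepoint values do not use baseline, and all ECG data are listed, so a flag can be checked by hand. The six may include placebo subjects, which is why only per-subject chances are given. All of this stands and keeps the point narrow.

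**Conclusion.** The point holds on the literal SAP text, in a narrow form. The stated rule gives Part 2 a reference from another period, the protocol's Day 1 pre-dose rule is overridden, and the change is undeclared. The identity in step 2 rests on no assumption and shows that flags can be created or hidden.

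The effect is confined to two descriptive QTcF categories in 6 subjects. Under the assumed SDs and no drug effect, the chance of a >30 ms flag is about 2.2 to 2.6 times as high with the Part 1 baseline, or 1.6 to 1.8 times once Follow-up is included. The >60 ms category is barely touched in that setting. The documents do not support a wider conclusion that the Part 2 ECG safety assessment is unreliable.

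**What to change.** In SAP 7.2, add:

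> For Part 2, baseline is the last observed value before the Part 2 dose; for Parts 1 and 3, it is the last observed value before the first dose in that part.

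Apply this to the >30 and >60 ms categories, and list any remaining departure from Protocol 10.3.4.2 in Section 10. If the SAP is closed, record the definition in the clinical study report and confirm which baseline the derivation used. If the counts are shown by fed state, SAP 8.2.4 should say so and name the time points that enter each column.

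The cost is one sentence and one derivation flag. The Part 2 pre-dose ECG is already in the schedule, so no new data are needed.
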